6.1 Inclusion Criteria

1) Signed Written Informed Consent

- a) Signed written informed consent must be obtained from the participants in accordance with requirements of the clinical facility's Institutional Review Board (IRB)/Independent Ethics Committee (IEC) prior to the initiation of any protocol-required procedures.

2) Type of Participant and Target Disease Characteristics

- a) Healthy participants as determined by no clinically significant deviation from normal in medical history, physical examination, vital signs, ECGs, and clinical laboratory determinations.
- b) Body weight will be between 60 and 100 kg, inclusive.

3) Age and Reproductive Status

- a) Males and Females, ages 18 or age of majority to 55 years, inclusive
- b) Women of childbearing potential (WOCBP) must have a negative serum pregnancy test within 24 hours prior to the start of study treatment.
- c) Women must not be breastfeeding
- d) WOCBP must agree to follow instructions for method(s) of contraception for the duration of treatment with abatacept plus 5 half-lives of abatacept (85 days) plus 30 days (duration of ovulatory cycle) for a total of 115 days post-treatment completion.
- e) Males who are sexually active with WOCBP must agree to follow instructions for method(s) of contraception ([Appendix 4](#)) for the duration of treatment with abatacept plus 5 half-lives of abatacept (85 days) plus the duration of spermatogenesis (90 days) for a total of 175 days after the last dose of study treatment. In addition, male participants must be willing to refrain from sperm donation during this time.
- f) Azoospermic males are exempt from contraceptive requirements. WOCBP who are continuously not heterosexually active are also exempt from contraceptive requirements, and still must undergo pregnancy testing as described in this section.

Investigators shall counsel WOCBP, and male participants who are sexually active with WOCBP, on the importance of pregnancy prevention and the implications of an unexpected pregnancy. Investigators shall advise on the use of highly effective methods of contraception, ([Appendix 4](#)) which have a failure rate of < 1% when used consistently and correctly.

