9.8.2 Immunogenicity Assessments

Table 9.8.2-1 lists the sampling schedule to be followed for immunogenicity assessments. Blood samples for determination of antibodies to abatacept and time-matched PK samples will be collected on Days 1, 15, 29, 57, and 71. Participants who seroconvert and continue to have a high titer at study discharge that is considered to be significantly increased versus baseline will be asked to return for follow-up assessment(s) for anti-abatacept antibodies approximately every 4 months until their titers and/or sero-status are judged to be stable by the investigator.

Table 9.8.2-1: Immunogenicity Sample Schedule

Study Day of Sample Collection	Event	Time (Relative To Start of Infusion of Abatacept Hour: Min)	Blood Sample for Immunogenicity
1	predose	00:00	X
15		336:00	X
29		672:00	X
57		1344:00	X
71		1680:00	X

A validated, sensitive, electrochemiluminescence assay (ECL) method will be used to detect anti-abatacept-antibodies with specificities to “CTLA4 and possibly Ig” and “Ig and/or Junction Region”.³⁴

Samples that are confirmed positive with specificity to “CTLA4 and possibly Ig” antibodies with the ECL immunogenicity assay will be further analyzed with a validated, in vitro, cell-based bioassay to determine whether the anti-abatacept-antibodies have neutralizing activity.

Record the date and time of sample collection so that compliance with the sampling schedule can be confirmed. Detailed instructions for the immunogenicity blood collection, labeling, processing, storage, and shipping will be provided to the site in the procedure manual.

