10.3.3 Other Analyses

10.3.3.1 Immunogenicity

Endpoint	Statistical Analysis Methods

anti-abatacept antibodies antibodies specific for ‘CTLA4 and possibly Ig’ and ‘Ig and/or Junction Region’
	
The incidence of laboratory-reported positive responses and the corresponding titer values will be listed by participant and by study day.
 
The frequency and percentage of positive abatacept-induced immunogenicity response will be summarized by treatment.

Lack of immunogenicity is defined as the absence of a positive antibody response generated against abatacept.

A participant is considered to have a positive abatacept-induced immunogenicity for ‘CTLA4 and possibly Ig’ or ‘Ig and/or Junction Region’ if 1 of the following criteria are met:

A missing baseline immunogenicity measurement and a positive laboratory-reported immunogenicity response after baseline.

- A negative laboratory-reported baseline immunogenicity response and a positive laboratory-reported immunogenicity response after baseline.
- A positive laboratory-reported baseline immunogenicity response and a positive laboratory-reported immunogenicity response after baseline that has a titer value strictly greater than the baseline titer value.

This definition will be applied for each antibody-reactivity separately. All other ECL immunogenicity measurements will be classified as negative.

[REDACTED]

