- ^b Hormonal contraception may be susceptible to interaction with the study treatment, which may reduce the efficacy of the contraceptive method. Hormonal contraception is permissible only when there is sufficient evidence that the IMP and other study medications will not alter hormonal exposures such that contraception would be ineffective or result in increased exposures that could be potentially hazardous. In this case, alternative methods of contraception should be utilized.
- ^c Intrauterine devices and intrauterine hormone releasing systems are acceptable methods of contraception in the absence of definitive drug interaction studies when hormone exposures from intrauterine devices do not alter contraception effectiveness

Less Than Highly Effective Contraceptive Methods That Are User Dependent

Failure rate of >1% per year when used consistently and correctly.

- Male or female condom with or without spermicide. Male and female condoms cannot be used simultaneously
- Diaphragm with spermicide
- Cervical cap with spermicide
- Vaginal Sponge with spermicide
- Progestogen-only oral hormonal contraception, where inhibition of ovulation is not the primary mechanism of action

Unacceptable Methods of Contraception

- Periodic abstinence (calendar, symptothermal, post-ovulation methods)
- Withdrawal (coitus interruptus).
- Spermicide only
- Lactation amenorrhea method (LAM)

CONTRACEPTION GUIDANCE FOR MALE PARTICIPANTS WITH PARTNER(S) OF CHILD BEARING POTENTIAL.

Male participants with female partners of childbearing potential are eligible to participate if they agree to the following during the treatment and until the end of relevant systemic exposure.

- Inform any and all partner(s) of their participation in a clinical drug study and the need to comply with contraception instructions as directed by the investigator.
- Male participants are required to use a condom for study duration and until the end of relevant systemic exposure defined as 85 days after the end of treatment plus an additional 90 days for a total of 175 days.
- Female partners of males participating in the study to consider use of effective methods of contraception until the end of relevant systemic exposure defined as 85 days after the end of treatment in the male participant.

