Participants with vital signs outside of a pre-specified range will also be listed.

The following criteria will be used to determine vital sign results that are outside of a pre-specified range, where changes from baseline are calculated as parameter value - baseline parameter value:

Heart Rate (bpm)	Value > 100 and change from baseline > 30, or Value < 55 and change from baseline < -15
Systolic BP (mmHg)	Value > 140 and change from baseline > 20, or Value < 90 and change from baseline < -20
Diastolic BP (mmHg)	Value > 90 and change from baseline > 10, or Value < 55 and change from baseline < -10
Respiration (breaths/min)	Value > 16 or change from baseline > 10
Temperature (°C)	Value > 38.3°C or change from baseline > 1.6°C

6.6.8 **Physical Examination Findings**

All physical examination abnormal findings will be listed per participant and visit.

6.7 **Pharmacokinetics**

The Pharmacokinetic (PK) population will be used for all listings. Evaluable PK population will be used for summary statistics and statistical analyses. Statistical analyses will be repeated excluding subjects with positive abatacept induced ADA responses. Analysis will include all valid analyte data for BMS-188667.

Subject serum concentration-time profiles will be listed and summarized by treatment and nominal collection time. Plot of individual serum concentration profiles over time will be provided. Overlay of individual serum concentration profiles over time will be provided by treatment. Plots of mean (+SD) serum concentration profiles versus time will be presented, for the first 24 hours and separately for the entire study duration on both linear and log-linear scale and both treatments will be superimposed on the same plot. Scatter plots of PK parameters for C_{max}, T-HALF, CLT, V_{ss}, AUC(0-28 day), AUC(0-T), and AUC(INF) will be produced for each treatment.

All individual PK parameters will be listed including any exclusions and reasons for exclusion. Summary statistics will be tabulated for each PK parameter by treatment. Geometric means and coefficients of variation will be presented for C_{max}, AUC(INF), AUC(0-T), AUC(0-28 day), CLT and V_{ss}. Medians and ranges will be presented for T_{max}. Means and standard deviations will be presented for other PK parameters (i.e., T-HALF). Decimal place specifications for summary statistics are described in Section 6.9.

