6.8.1 Immunogenicity

On Day 1, the immunogenicity sample should be drawn at predose.

Participants who seroconvert and continue to have a high titer at study discharge that is considered to be significantly increased versus baseline will be asked to return for follow-up assessment(s) for anti-abatacept antibodies approximately every 4 months until their titers and/or sero-status are judged to be stable by the investigator.

Lack of immunogenicity is defined as the absence of a positive antibody response generated against abatacept. A participant is considered to have a positive abatacept-induced immunogenicity for “CTLA4 and possibly immunoglobulin (Ig)” and “Ig and/or Junction Region” if one of the following criteria are met:

1. A missing baseline immunogenicity measurement and a positive laboratory-reported immunogenicity response after baseline.

2. A negative laboratory-reported baseline immunogenicity response and a positive laboratory-reported immunogenicity response after baseline.
3. A positive laboratory-reported baseline immunogenicity response and a positive laboratory-reported immunogenicity response after baseline that has a titer value strictly greater than the baseline titer value.

This definition will be applied for each antibody-reactivity separately. All other electrochemiluminescence (ECL) immunogenicity measurements will be classified as negative.

The incidence of laboratory-reported positive responses and the corresponding titer values will be listed by participant and by study day. The frequency and percentage of positive, abatacept-induced immunogenicity response will be summarized by treatment.

Titer will be listed.

The number and percentage of subjects with a positive neutralizing antibody response will be summarized by treatment group and study day. The summary will include all subjects with a positive abatacept-induced immunogenicity response.

Neutralizing antibody data will be listed.

[REDACTED]

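### Non-positive antibody results are classed as negative whatever the time-matched abatacept level, so any response still masked through Day 71 would count as no response

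*SAP*

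**What the plan says.** Immunogenicity of Treatment A versus Treatment B is a secondary objective (Protocol Table 4-1, SAP Table 3-1). Protocol 9.8.2 sets the sampling: "Blood samples for determination of antibodies to abatacept and time-matched PK samples will be collected on Days 1, 15, 29, 57, and 71". The Day 1 sample is pre-dose. Further antibody samples, about every 4 months, are planned only for participants who seroconvert and still have a high titer at discharge.

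SAP 6.8.1 and Protocol 10.3.3.1 give the same three criteria for a positive abatacept-induced response: positive after a missing baseline, positive after a negative baseline, or positive with a titer above a positive baseline. The SAP then closes the rule with "All other electrochemiluminescence (ECL) immunogenicity measurements will be classified as negative"; the protocol has "All other ECL immunogenicity measurements will be classified as negative". The planned summary is the frequency and percentage positive by treatment. The visible text gives no inconclusive category and no drug-tolerance limit for either the ECL assay or the neutralizing bioassay.

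Antibody status also feeds the PK analysis. SAP 6.7 states: "Statistical analyses will be repeated excluding subjects with positive abatacept induced ADA responses".

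On how long the drug persists, Protocol 6.1 uses "5 half-lives of abatacept (85 days) plus 30 days (duration of ovulatory cycle) for a total of 115 days". Appendix 4, in its contraception guidance for male participants, sets the exposure period as "until the end of relevant systemic exposure defined as 85 days after the end of treatment". For condom use it extends this by 90 days, which gives 175.

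**The concern.** Circulating drug can bind anti-drug antibody and hide it from an assay. Above the assay's drug tolerance, a non-positive result means that antibody could not be measured, not that it was absent. The rule cannot separate these two cases, although the concentrations needed to do so are collected. Read literally, it would even turn a result that the laboratory reports as inconclusive into a negative.

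Two outputs are exposed. The incidence in each arm could be too low, and if masking is equal in both arms, any true difference between the processes shrinks by the same factor. In addition, a participant with a masked response would remain in the PK repeat that is meant to be free of antibody-positive participants.

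**Working it through.** **Inputs.** Five half-lives = 85 days (Protocol 6.1, Appendix 4). Antibody samples at 336, 672, 1344 and 1680 h (Protocol Table 9.8.2-1). Dose 750 mg IV. About 70 participants per arm (Protocol 5.2).

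**The plan's own figures.** 85 + 30 = 115 days; 85 + 90 = 175 days; 1680/24 = 70 days. All three reproduce. The implied half-life is 85/5 = 17 days.

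**Drug remaining.** Fraction = 0.5^(t/17), assuming single first-order decay.

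**Concentration (assumed).** The documents give no distribution volume. Taking one compartment and a volume V of 3 to 8 L, concentration = (750/V) × fraction. The starting level is 750/3 = 250 µg/mL or 750/8 = 93.75 µg/mL.

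| Study day | Days after dose | Half-lives | Remaining | V = 3 L (µg/mL) | V = 8 L (µg/mL) |
|---|---|---|---|---|---|
| 15 | 14 | 0.82 | 56.5% | 141 | 53 |
| 29 | 28 | 1.65 | 31.9% | 80 | 30 |
| 57 | 56 | 3.29 | 10.2% | 25.5 | 9.6 |
| 71 | 70 | 4.12 | 5.8% | 14.4 | 5.4 |

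None of the four scheduled post-dose samples reaches 85 days. The last falls 85 − 70 = 15 days short, with 5.8% remaining against 0.5^5 = 3.1% at five half-lives.

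**Sensitivity to half-life (assumed values).** At Day 71 the fraction remaining is 2.4% for 13 days, 3.1% for 14, 8.8% for 20 and 14.4% for 25. Day 71 reaches five half-lives only if the half-life is 70/5 = 14 days or less.

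**When would a drug-level condition change anything?**
- *Sample level.* A label can change only if tolerance is below the concentration in that sample. The highest modelled value is 141 µg/mL (Day 15, 3 L), so above that no label changes.
- *Participant level.* If one conclusive negative is enough, the sample with the lowest drug level decides. With a Day 71 sample, results change only if tolerance is below about 14 µg/mL at 3 L, or 5 µg/mL at 8 L. If only 30% of the initial level enters the terminal phase, these limits fall to 0.3 × 14.4 = 4.3 and 0.3 × 5.4 = 1.6 µg/mL.

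**Size of the effect if masking occurs (illustration).** Let m be the assumed share of true positives masked at every sample. Observed rate = true rate × (1 − m). A true 10% (7 of 70) reads 7.5%, 5.0% or 2.5% at m = 25%, 50% or 75%. With the same m in both arms, the absolute difference shrinks by the same factor (1 − m).

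**The case against.** The strongest reply is that drug being present is not masking. The protocol calls the ECL assay validated and sensitive, and it may tolerate 6% of the drug at Day 71 with ease. The 85 days comes from contraception text, not from an assay statement. A tolerance limit or handling rule may stand in the redacted text after both immunogenicity sections, or in the assay report. Immunogenicity is summarised descriptively, with no test or margin, and dose, schedule and assay are the same in both arms. ECL results and concentrations are both listed by participant, so a reader could cross-check them.

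Much of this stands, and it rules out several stronger readings:

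- A reader might infer that every antibody sample is affected. The Day 1 sample is pre-dose, and the conditional 4-monthly samples come later than 85 days.
- A reader might infer that antibodies are in fact being masked. Without the tolerance and the actual concentrations, the documents cannot show that.
- A reader might infer that a masked response is never tested again. A response masked on Day 15 is re-tested on Days 29, 57 and 71, while the drug falls about 10-fold (56.5/5.8). Only a response still masked at Day 71 escapes, because later sampling is triggered by seroconversion.
- A reader might expect neutralizing positives to rise by study day simply because drug falls. The bioassay is run only on samples already confirmed positive for one specificity, and true responses may also develop with time.

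Two things survive. The sentence that sends everything else to negative is an explicit rule, so any redacted provision to the contrary would have to be reconciled with it. And cross-checking listings by hand is no substitute for a pre-specified category in the by-treatment table and in the PK repeat.

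**Conclusion.** The point holds as a cheap improvement. By the plan's own figures, all four scheduled post-dose antibody samples are drawn inside the 85-day exposure window, and the negative class carries no drug-level condition despite "time-matched PK samples will be collected on Days 1, 15, 29, 57, and 71". Any response masked through Day 71 would count as negative.

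The practical size is unknown and may be nil. Participant-level results change only if tolerance is below about 14 µg/mL at best (5 µg/mL at 8 L). That rests on the 17-day half-life, one compartment, the assumed 3 to 8 L and an available Day 71 sample. A participant whose last sample is earlier has a higher limit: 25.5 µg/mL at Day 57 with 3 L, for example.

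A reader might also infer a threat to the main conclusion. There is none: biocomparability rests on Cmax and AUC(INF) in the Evaluable PK Population, and antibody status enters only through the repeat analysis.

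**What to change.** In SAP 6.8.1, with matching wording in Protocol 10.3.3.1:

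1. Keep the three positive criteria. Keep as negative a post-dose positive whose titer is not above a positive baseline; the present catch-all sentence covers that case, and the replacement must not drop it.
2. State the validated drug tolerance of the ECL assay. Label a laboratory-negative post-dose result *inconclusive* when the time-matched abatacept concentration exceeds it.
3. Call a participant inconclusive only if no sample meets the positive criteria and no post-dose sample is a conclusive negative.
4. Report positive, negative and inconclusive counts by treatment beside the planned percentage, and give percent positive among conclusive participants as well.
5. Label non-positive neutralizing results in the same way, using that assay's own tolerance.
6. In SAP 6.7, add a PK repeat restricted to conclusive negatives.

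The cost is SAP and protocol wording and one merge of antibody results with concentrations already collected; no new sample or visit is needed. The conclusive denominator may be smaller. The change recovers no masked positive; it only stops unmeasurable results being counted as absence of antibody. If tolerance proves ample, the tables will show no inconclusive participants and the negative finding will be better supported.

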3 OBJECTIVES AND ENDPOINTS

Table 3-1: Objectives and Endpoints

Objectives	Endpoints

Primary
 
 To compare the PK of the abatacept drug product converted from drug substance by a new drug substance process (Treatment A) relative to the current drug substance process (Treatment B) following a single dose (750 mg) IV infusion in healthy participants. 	
 Cmax and AUC(INF) of abatacept

Secondary
 
 To assess the safety of a single dose (750-mg) IV infusion of the abatacept drug product converted from drug substance by a new drug substance process (Treatment A) versus drug substance by the current drug substance process (Treatment B). To assess the immunogenicity of abatacept drug product converted from drug substance by a new drug substance process (Treatment A) versus drug substance by the current drug substance process (Treatment B). To characterize the PK of abatacept drug product converted from drug substance by a new drug substance process (Treatment A) versus drug substance by the current drug substance process (Treatment B). 	
 Safety assessments will be based on medical review of AE reports, vital sign measurements, ECGs, physical examinations, and clinical laboratory tests. Immunogenicity determination will be based on the incidence of laboratory-reported positive responses and titers of anti-abatacept antibodies specific for “CTLA4 and possibly Immunoglobulin (Ig)” and “Ig and/or Junction Region.” Time of maximum observed concentration (Tmax), area under the serum concentration-time curve from time zero to time of the last quantifiable concentration (AUC(0-T)), AUC(0-28 day), CLT, Vss, and T-HALF of abatacept

[Redacted]
	
[Redacted]

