6.9 Conventions

EmBARC (Enhanced Biometric Analysis & Reporting Capability) standard time windowing, imputation rules, and counting rules will be applied.

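### Does the neutralizing-antibody percentage in SAP 6.8.1 need a stated rule for participants whose samples never go to the bioassay?

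*SAP*

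**What the plan says.** SAP 6.8.1 plans this table: "The number and percentage of subjects with a positive neutralizing antibody response will be summarized by treatment group and study day". The next sentence sets who is in it: "The summary will include all subjects with a positive abatacept-induced immunogenicity response".

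Whether a participant has an induced response is decided per reactivity. The SAP states "This definition will be applied for each antibody-reactivity separately", and Protocol 10.3.3.1 joins the two with 'or': "positive abatacept-induced immunogenicity for ‘CTLA4 and possibly Ig’ or ‘Ig and/or Junction Region". A participant who was already positive at baseline counts only if a later positive sample "has a titer value strictly greater than the baseline titer value".

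Testing is narrower. Protocol 9.8.2 says "Samples that are confirmed positive with specificity to “CTLA4 and possibly Ig” antibodies with the ECL immunogenicity assay will be further analyzed" in the cell-based neutralizing assay. No visible text sends samples positive only for 'Ig and/or Junction Region' to that assay.

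Three other places bear on the point:
- SAP 6.9 defers to the sponsor's EmBARC conventions: "standard time windowing, imputation rules, and counting rules will be applied".
- SAP 7 leaves the details of tables to a Data Presentation Plan.
- SAP 3 words the secondary endpoint without neutralizing antibodies: "Immunogenicity determination will be based on the incidence of laboratory-reported positive responses and titers of anti-abatacept antibodies".

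**The concern.** Inclusion is by participant and covers either reactivity. Testing is by sample and covers one. Three groups therefore do not line up.

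- Participants with an induced response only to 'Ig and/or Junction Region' are in the table with no bioassay result.
- On a by-day row, so are participants whose 'CTLA4 and possibly Ig' positive sample fell on another day.
- In the other direction, a participant positive for 'CTLA4 and possibly Ig' at baseline, whose later positive titer does not rise, is bioassayed but has no induced response to that reactivity. The result may fall outside the table.

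The rule that classifies everything else as negative covers measurements by the electrochemiluminescence (ECL) assay, not the bioassay, so it does not settle the first two cases. The percentage appears by treatment under an objective that sets the new process against the current one. If untested participants stay in the denominator, two arms with the same neutralizing results among those tested could show different percentages.

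**Working it through.** The documents state no neutralizing-antibody figure, so there is nothing to reproduce. The check is a reading of the passages plus simple proportions with assumed counts.

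**1. Can an untested participant be in the table?** Yes. SAP 6.8.1 joins the reactivities with 'and', which could be read as requiring both. Its own sentence on separate application, and the protocol's 'or', rule that reading out.

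**2. Effect of the denominator.** Let N be the participants included, T those tested, X those neutralizing-positive, and f = (N − T)/N the untested share. Then

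X/N = (X/T) × (T/N) = (X/T) × (1 − f).

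The documents do not give f. Over a range, the factor is 1 at f = 0, 0.75 at 25%, 0.5 at 50% and 0.25 at 75%.

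**3. By-day rows.** There are four post-dose sampling days (15, 29, 57, 71; Protocol 9.8.2). If included participants have a tested sample on k of the four on average, the mean of T_d/N is k/4. The by-day percentages then average k/4 of the pooled rate among tested samples: 0.25 at k = 1, 0.5 at k = 2, 1 at k = 4. This compares two different quantities. One is the share of induced responders with neutralizing activity shown on that day. The other is the share of tested samples that neutralize. Neither is an error for the other.

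**4. An adverse illustration (all counts assumed).** Each arm has 4 tested and 2 neutralizing-positive. Arm A has 12 induced responders and arm B has 6; 70 per arm are treated with post-dose data.

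| Quantity | A | B |
|---|---|---|
| Untested share f | 8/12 = 67% | 2/6 = 33% |
| Neutralizing / all induced | 2/12 = 16.7% | 2/6 = 33.3% |
| Neutralizing / tested | 2/4 = 50% | 2/4 = 50% |
| Induced / treated | 12/70 = 17.1% | 6/70 = 8.6% |
| Neutralizing / treated | 2/70 = 2.9% | 2/70 = 2.9% |

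The contrast of 16.7% with 33.3% comes from the chosen imbalance of 12 against 6. That imbalance appears in the induced-response table, which SAP 6.8.1 plans separately. The two tables multiply back to the same answer in each arm: 12/70 × 2/12 = 2/70 and 6/70 × 2/6 = 2/70. The neutralizing table would also show the equal counts, 2 and 2, because it gives numbers as well as percentages.

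**5. Would a tested-only denominator do better?** It matches the assay but can be tiny. For 2 of 4 the exact 95% interval is 6.8% to 93.2%.

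**6. The baseline-positive participant.** SAP 6.8.1 limits the table to induced responses, and a positive without a titer rise is not one by the stated definition. The bioassay result is still listed. Testing more samples than are summarised is not a contradiction.

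**The case for a change.** The best case for a change is that the visible SAP does not say whether untested participants count as negative, are shown as not tested, or are left out. This study tests two reactivities but sends only one on to the bioassay, so a general counting convention may not cover the case. The EmBARC rules, the Data Presentation Plan and the redacted text after the sentence on listing neutralizing data cannot be seen, so none can be relied on to hold the answer. Readers compare percentages across arms more readily than they read listings, and one sentence would cost almost nothing.

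The silence is real, and that part stands. It does not make the table unsound. Saying who is in a summary does not fix the denominator of every by-day percentage. Under either natural choice, all induced responders or those tested, the result is interpretable once the table shows its N. Which to display is partly a trade-off: the first is steadier but mixes in untested participants; the second matches the assay but may rest on a handful of people. An analyst building the table will see blank bioassay results and has to label them, and table specifications are the usual place for that label.

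**Conclusion.** No change to the plan follows. The mismatch between who is summarised and which samples are tested is correctly observed. It leaves one counting detail unstated in a descriptive table.

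Its numerical effect is a factor of (1 − f) on one percentage. That is nothing if every induced responder has a tested sample and a halving if half do not. The value of f, the by-day k and the arm counts used above are all assumptions, because the documents give no expected rates. No test, margin or decision uses the percentage. Neutralizing antibodies are not in the wording of the secondary endpoint, and the Cmax and AUC(INF) comparison is unaffected.

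The planned counts, the separate induced-response frequencies by treatment, and the listings of responses, titers and neutralizing results let a reader form any denominator. Analysts following this plan would still reach sound results.
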